#### Phase 2 Study AACG ARIA events

Study AACG was a Phase 2, double-blind, placebo-controlled study in participants with early symptomatic AD with intermediate brain tau burden. In Study AACG, ARIA (-E, -H, or both) was observed in a higher percentage of participants treated with donanemab, compared to participants treated with placebo. A majority of ARIA-E and ARIA-H events were first observed within 12 weeks of treatment initiation, with most events observed by 24 weeks.

ARIA-E occurred in 26.7% of participants treated with donanemab, with 6.1% of cases being symptomatic. Symptoms associated with ARIA-E included, but were not limited to, worsening of headache, altered mental status, confusion, and difficulty expressing themselves. Serious symptomatic ARIA-E requiring hospitalization occurred in 1.5% of participants treated with donanemab.

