# 4.2. Scientific Rationale for Study Design

Study AACQ is a multicenter, randomized, double-blind study of donanemab in participants with early symptomatic AD, where early symptomatic AD refers to the combination of 2 stages, mild cognitive impairment and mild AD dementia. This study is intended to assess

- alternate donanemab dosing regimens that could potentially reduce the risk of ARIA-E frequency, severity, symptoms
- baseline and treatment response characteristics, including MRI and blood-based biomarkers, that might predict risk of ARIA-E, and
- amyloid lowering of alternate dosing regimens.

Characterizing the frequency, severity, onset, and resolution of ARIA events, in relation to dosing, is an important overall goal in understanding the benefit/risk of using amyloid lowering treatments for patients with early symptomatic AD.

In Study AACQ, all participants will receive donanemab, but at different dose levels and frequency of dosing (See Section 4.1.1.). Placebo is given at specific visits to preserve the blind for the different dosing regimens.

Study AACQ allows all participants to continue or change their symptomatic AD standard of care concomitant medications during the study.

Physical and neurological examinations, MRI assessments, and assessments of SIB are included to facilitate a comprehensive safety evaluation, in addition to AE reporting, safety measures such as laboratory assessments, immunogenicity testing, vital signs, and weight monitoring.

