# 8.3. Adverse Events, Serious Adverse Events, and Product Complaints

The definitions of the following events can be found in Section 10.3:

- AEs
- SAEs, and
- PCs.

These events will be reported by the participant (or, when appropriate, by a caregiver, surrogate, or the participant's legally authorized representative).

The investigator and any qualified designees are responsible for detecting, documenting, and recording events that meet these definitions and remain responsible for following up events that are serious, considered related to the study intervention or study procedures, or that caused the participant to discontinue the study intervention.

Care will be taken not to introduce bias when detecting events. Open-ended and non-leading verbal questioning of the participant is the preferred method to inquire about event occurrences.

After the initial report, the investigator is required to proactively follow each participant at subsequent visits or contacts. All SAEs and AEs of special interest as defined in Section 8.3.3 will be followed until resolution, stabilization, the event is otherwise explained, or the participant is lost to follow-up (as defined in Section 7.3). For PCs, the investigator is responsible for ensuring that follow-up includes any supplemental investigations as indicated to elucidate the nature and/or causality. Further information on follow-up procedures is provided in Section 10.3.

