#### Guidance if ARIA is present

If ARIA is present, repeat MRIs are recommended every 4 to 6 weeks until resolution of ARIA-E or stabilization of ARIA-H.

For asymptomatic or mild symptoms, the participant can be observed; for moderate symptoms associated with ARIA-E, the use of oral or IV steroids can be considered. In the case of severe symptoms associated with ARIA-E, it is recommended to hospitalize the participant for close observation and consider the use of IV steroids such as high-dose dexamethasone or a similar agent. See Manual of Operations and Section 7.1.2 for more guidance.

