4.1. General Considerations

As 4 donanemab dosing regimens including the standard one are available for Study AACQ, any safety or biomarker analysis will involve 3 comparisons: 1) dose skipping vs. standard dosing; 2) titration vs. standard dosing; 3) Cmax (concentration maximum) vs. standard dosing.

Safety analyses will include subjects who are randomized to study treatment and who take at least 1 dose of treatment. Subjects will be analyzed according to the treatment arm to which they were assigned.

Unless otherwise specified, analyses for ARIA events are based on MRI findings or AE (adverse events) reporting. ARIA safety analyses will cover both ARIA-E and ARIA-H events by Week 24 as well as by Week 52. Bayesian logistic regression method is proposed to obtain a posterior distribution regarding relative risk reduction in ARIA-E or ARIA-H at Week 24 or 52 for each of 3 comparisons mentioned above. The details of logistic regression model, prior elicitation, and computation for the posterior distribution will be presented in Section 4.3.2. From each derived posterior distribution of RD_{21} , RD_{31} , and RD_{41} , summary statistics will be reported which include posterior mean, posterior median, posterior mode, a 2-sided equal-tailed 95% posterior interval (often cited as credible interval in Bayesian literature), and a posterior probability of achieving a minimum of 20% relative risk reduction in ARIA-E.

Frequentist methods will be used for the rest of the study objectives. All frequentist tests will be conducted at a 2-sided alpha level of 0.05; 2-sided confidence intervals (CIs) will be displayed with a 95% confidence level.

Unless otherwise noted baseline is defined as the last measurement prior to dosing. When change from baseline is assessed, subjects will only contribute to the analysis if both a baseline and a post-baseline measurement are available. Endpoint is the last non-missing post-baseline measurement within the time period for the given analysis.

To allow for evaluation of the primary and secondary hypotheses at 24 and 52 weeks, database locks and the assessments of corresponding primary and secondary objectives are expected to occur after all participants in the Safety Analysis Set have had the opportunity to complete visits 12 and 19 including PET and MRI assessments. The sponsor may choose not to have a separate database lock after visit 19 and wait to perform the analyses for 52-week data until the final database lock.

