4.4. Secondary Endpoints Analysis

4.4.1. 12-month and 18-month incidence of ARIA-E

For the analysis of 52-week ARIA-E incidence, all 4 scheduled MRIs (weeks 4, 12, 24, 52) and unscheduled MRI data as well as treatment-emergent cluster data will be used first to obtain descriptive statistics including total number and proportion of patients with ARIA-E in 1-year in AACQ and by treatment arm.

Like the method for analyzing the primary endpoint, a Bayesian logistic regression will be applied before answering whether relative risk reduction of ARIA-E in 52 weeks is significant comparing the dosing skip arm with standard dosing arm, or comparing the titration arm with standard dosing arm, or comparing the Cmax arm with standard dosing arm. A diffuse prior will be used for each slope parameter in this Bayesian logistic regression model and a mixture prior for the intercept parameter will be elicited from 52-Week ARIA-E outcome in AACI-Addendum 9 study. The probability that one alternative dosing arm has a minimum of 20% risk reduction in ARIA-E in one year compared to the standard dosing arm will be derived from each of 3 simulated posterior distributions in relative risk reductions. In addition, the sensitivity analyses proposed in Section 4.3.3 will be used for 52-week analysis of ARIA-E.

All scheduled postbaseline MRIs (weeks 4, 12, 24, 52, and ED) and unscheduled MRI data as well as treatment-emergent cluster data will be analyzed for ARIA-E events up to Week 76 using the framework in Section 4.3.2 or following the descriptions for the analysis of 1-year incidence of ARIA-E.

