4.6.6. Amyloid-Related Imaging Abnormalities (ARIA)

ARIA incidence was discussed in Section 4.3, Section 4.4.1, and Section 4.4.3. Severity of ARIA events was covered in Section 4.4.3.

Unless otherwise specified, safety analyses of ARIA events are based on centrally read MRI findings from both scheduled and unscheduled visits. Where applicable, ARIA-E summaries will be presented for symptomatic and asymptomatic ARIA-E. ARIA-H summaries will be presented by ARIA-H microhemorrhage and ARIA-H superficial siderosis. Macrohaemorrhage will be described separately and will not be included in the ARIA-H category.

An overview of ARIA incidence by treatment arm from safety analysis set will be presented using frequency and percentage of patients with any ARIA (ARIA-E or ARIA-H), ARIA-E, and ARIA-H as defined by safety MRIs or treatment-emergent AE clusters. The proportion of the patients with serious adverse events of ARIA, ARIA-E, and ARIA-H with or without ARIA-E will be summarized via treatment arm. The frequency and percentage of ARIA-E will be further

broken out by asymptomatic vs. symptomatic and by APOE genotype. The frequency and percentage of subjects with ARIA-H microhemorrhage, ARIA-H superficial siderosis, and macrohemorrhage will be further broken out by APOE genotype. A sensitivity analysis of overview of ARIA incidence will be performed utilizing per-protocol analysis set.

A severity shift table of ARIA-E, ARIA-H microhemorrhage, and ARIA-H superficial siderosis severity from baseline to Week 76 by visit and by treatment arm will be presented.

To investigate the onset of the first ARIA-E or ARIA-H event among different dosing regimens, Kaplan-Meier plots will be presented using safety analysis set. Besides Kaplan-Meier plots, histograms of the onset of the first ARIA-E or ARIA-H based on safety MRI may be provided to visually inspect timing of the first ARIA event across treatment arms.

From safety analysis set, mean and median duration before the resolution of ARIA-E or the mean and median duration of ongoing ARIA-E events for each dosing regimen will be derived.

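### SAP 4.6.6 summarises ARIA-E duration without treating ongoing events as censored, which can understate time to resolution, mainly at an early lock; a Kaplan-Meier estimate should be added (minor).

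*SAP*

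**What the plan says.** SAP 4.6.6 closes with the duration summary: the "mean and median duration before the resolution of ARIA-E or the mean and median duration of ongoing ARIA-E events for each dosing regimen". It does not say whether both parts will be shown, at which lock, how an unresolved event enters, or which MRI dates the resolution.

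The same section does use a method for censored data, but only for onset: "To investigate the onset of the first ARIA-E or ARIA-H event among different dosing regimens, Kaplan-Meier plots will be presented using safety analysis set". The log-rank and Cox options in Protocol 9.3.3, and the censoring rule stated there, also concern first occurrence. Neither document has a counterpart for resolution.

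Protocol 4.2 gives resolution some weight: "Characterizing the frequency, severity, onset, and resolution of ARIA events, in relation to dosing, is an important overall goal".

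Follow-up of an event comes from Protocol 8.3.3.1, under which "repeat MRIs are recommended every 4 to 6 weeks until resolution of ARIA-E or stabilization of ARIA-H", and from Protocol 8.3: "All SAEs and AEs of special interest as defined in Section 8.3.3 will be followed until resolution" (or until it stabilises, is otherwise explained, or the participant is lost). Scheduled MRIs after the first infusion fall at Weeks 4, 12, 24 and 52. After Week 52 the schedule has none except at early discontinuation. SAP 4.1 places the locks "after all participants in the Safety Analysis Set have had the opportunity to complete visits 12 and 19 including PET and MRI assessments", with the Week 52 lock optional, followed by a final lock.

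**The concern.** At any lock some ARIA-E events may still be open. Sorting events by whether they have closed, then averaging inside each group, selects on the outcome. The closed group is enriched for short events, and the open group holds truncated times. Neither number answers how long ARIA-E lasts under a given regimen.

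Some open events are to be expected. One first seen on the Week 24 MRI cannot be recorded as resolved until a repeat scan some 4 to 6 weeks later. Repeat scans are recommended, not required. A participant who withdraws with unresolved ARIA-E stays open at every later lock; SAP 5 assumes 10% will not reach the primary lock, and SAP 6.5 singles out withdrawal as a worry.

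A by-regimen duration is likely to be read as evidence on the design rationale. Protocol 4.3 partly justifies the 8-week interval by the hypothesis that it gives asymptomatic ARIA time to resolve, and Protocol 7.1.2 ties restarting treatment to resolution. A duration that depends on the lock date is a poor basis for that reading.

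**Working it through.** The documents state no duration or resolution figure, so there is nothing to reproduce. What follows is an illustration.

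**From the documents.** Repeat MRI every 4 to 6 weeks (Protocol 8.3.3.1; 5 used here). Scheduled MRIs to Week 24 at Weeks 4, 12 and 24 (SAP 4.3.1). About 200 participants per arm; ARIA-E rates of 18.5% and 11.1% (SAP 5), so 200 × 0.185 = 37 and 200 × 0.111 ≈ 22 events per arm by Week 24.

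**Assumed.** Exponential true duration with median m = 6, 8 or 12 weeks, the same in both arms. First detection at Weeks 4/12/24 in 30/45/25% (early-onset arm) or 15/35/50% (late-onset arm). Resolution dated at the first 5-weekly scan that shows it. Every participant cut at the same study week C.

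**Formulas.** Let q = 2^(−5/m). The MRI-dated duration is 5k weeks with probability q^(k−1)(1−q), so its mean over all events is 5/(1−q): 11.4, 14.2 and 19.9 weeks. An event first seen at week d, with weight w_d, has n_d = floor((C−d)/5) repeat scans before the cut.
- Resolved share R = Σ w_d (1 − q^n_d)
- Resolved-only mean = Σ w_d Σ(k=1..n_d) 5k q^(k−1)(1−q) / R

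**Worked case** (m = 6, early arm, C = 24). q = 0.5612; n = 4, 2, 0. R = 0.30(1 − 0.099) + 0.45(1 − 0.315) = 0.578. Numerator = 0.30 × 8.28 + 0.45 × 4.66 = 4.58. Mean = 4.58/0.578 = 7.9 weeks against 11.4, a shortfall of 30.5%.

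| m | Mean, all events | Cut (week) | Resolved, early / late | Resolved-only mean, early / late | Shortfall, early / late | Gap (weeks) |
|---|---|---|---|---|---|---|
| 6 | 11.4 | 24 | 58% / 37% | 7.9 / 7.7 | 30.5% / 32.8% | 0.3 |
| 6 | 11.4 | 52 | 98% / 97% | 10.8 / 10.5 | 5.4% / 7.9% | 0.3 |
| 6 | 11.4 | 76 | 100% / 100% | 11.3 / 11.3 | 0.6% / 0.9% | 0.0 |
| 8 | 14.2 | 24 | 51% / 33% | 8.4 / 8.1 | 40.9% / 43.1% | 0.3 |
| 8 | 14.2 | 52 | 95% / 93% | 12.6 / 12.1 | 11.5% / 15.2% | 0.5 |
| 8 | 14.2 | 76 | 99% / 99% | 13.9 / 13.8 | 2.6% / 3.3% | 0.1 |
| 12 | 19.9 | 24 | 40% / 26% | 9.0 / 8.6 | 55.0% / 56.9% | 0.4 |
| 12 | 19.9 | 52 | 87% / 84% | 15.1 / 14.1 | 24.5% / 29.0% | 0.9 |
| 12 | 19.9 | 76 | 97% / 96% | 18.0 / 17.6 | 9.9% / 11.7% | 0.4 |

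**Medians.** The true MRI-dated medians are 10, 10 and 15 weeks. At Week 24 the resolved-only medians are 5, 5 and 10; at Week 76 they equal the truth. In every row they are the same in both arms.

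**Kaplan-Meier on the same scale.** Among events still open and scanned, the chance of resolution at each scan is 1−q, so S(5k) = q^k whatever the onset mix or cut. The median is the first 5k with q^k ≤ 0.5. That is k = 2 (0.315), k = 2 (0.420) and k = 3 (0.420), or 10, 10 and 15 weeks in both arms at every cut.

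**Gap against noise.** With 22 events, the standard error of the late arm's resolved-only mean is SD/√(22R). For m = 6 at Week 24 it is 3.7/√8.2 = 1.3 weeks; for m = 12 at Week 52 it is 9.1/√18.4 = 2.1 weeks. The corresponding gaps are 0.3 and 0.9.

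**Sensitivity.** This used a different assumed onset mix (35/40/20/5% against 15/35/35/15% at Weeks 4/12/24/52) and exact dating of resolution.
- Exponential, median 10 (mean 14.4): resolved-only means, early / late, of 6.6 / 6.1 at Week 24 and 13.4 / 12.8 at Week 76. Kaplan-Meier medians were 9.9 to 10.1 throughout.
- Exponential, median 16 (mean 23.1): 18.5 / 17.4 at Week 76.
- Weibull shape 2, median 6 or 10: no visible bias from Week 52 on.

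**The case against.** The strongest reply is that few events will be open when it matters. The duration sentence sets no cut-off, and the shift table in the same section runs to Week 76. ARIA is an event of special interest, followed to resolution or stabilisation. In the earlier Phase 2 study, "A majority of ARIA-E and ARIA-H events were first observed within 12 weeks of treatment initiation, with most events observed by 24 weeks". With staggered entry, many participants will be well past Week 24 when the last one reaches it. All of this stands: a uniform Week 24 cut is a worst case, and at the final lock the bias is small unless durations are long or dropout is material.

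A reader might infer that time to resolution is certain to be too short in every arm. The documents do not support that. The result depends on how many events are open, and with less dispersed durations the bias vanishes by Week 52. Dating resolution at the next scan also lengthens recorded durations relative to biological ones: with an exponential median of 6 weeks, the resolved-only mean at Week 76 is 11.3 weeks against a biological mean of 8.7. The understatement holds on the MRI-dated scale.

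A reader might also infer that an alternative regimen will look faster to resolve because its events start later. No passage predicts later onset: Protocol 4.2 and 4.3 speak of frequency, severity and symptoms. Fewer events alone do not shift their timing, the illustrated gap is below one standard error, and the planned medians showed no gap between arms.

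Finally, giving ongoing events their own summary discloses them, and resolution is not a listed endpoint. Both are fair, and both lower the severity. They do not turn either figure into an estimate of duration.

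**Conclusion.** The concern holds in a limited form. As written, SAP 4.6.6 yields no valid estimate of time to ARIA-E resolution per regimen, although Protocol 4.2 names resolution in relation to dosing as an important goal.

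On the MRI-dated scale, with exponential durations of median 6 to 12 weeks, the mean over resolved events can fall short by about 30 to 57% at a uniform Week 24 cut and by at most about 12% by Week 76. Longer durations would leave more (about 20 to 25% at Week 76 with a median of 16 weeks, from 18.5 and 17.4 against 23.1). If onset timing differed between regimens, a spurious gap of about 0.3 to 0.9 weeks could arise at Weeks 24 to 52. The duration distribution, onset mix and common cut are assumptions.

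Severity is minor. The output is descriptive, carries no test or decision, and has no bearing on the primary endpoint, sample size or power.

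**What to change.** Add to, or replace, the last sentence of SAP 4.6.6 with wording such as:

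*For each regimen, time from the first MRI showing ARIA-E to the first MRI showing its resolution will be estimated by Kaplan-Meier, using each participant's first episode. Resolution is dated at the first MRI that shows it. Unresolved events are censored at the last MRI. The median and quartiles with 95% CIs, and the numbers of events resolved and unresolved, will be reported.*

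The planned means and medians may stay as description if the counts stand beside them. The SAP should also name the lock or locks at which the output is produced. At a Week 24 cut the upper quartile may not be estimable: with m = 12, S(20) = 0.749^4 = 0.315, still above 0.25.

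This estimate does not model interval censoring between scans; the stated dating rule makes that limit explicit and equal across arms. The cost is one SAP sentence and one Kaplan-Meier output from data already collected, with no extra scans or visits.

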4.6.7. Hypersensitivity/Infusion Related Reactions

Section 4.5.3 described ways to explore whether alternative dosing regimen will impact IRR frequency and severity. In this subsection, both hypersensitivity and IRRs will be analyzed and summarized from safety analysis set. Hypersensitivity and IRRs will be broken out between potential immediate (defined as TEAEs occurring on the date of infusions, or for which a hypersensitivity follow-up form indicates the event occurred within 24 hours of study drug administration) and potential non-immediate (defined as TEAEs that are not immediate but occur prior to the administration of a subsequent infusion).

The AE database will be searched using predefined SMQs to identify preferred terms (PTs) that map hypersensitivity events or IRRs in both potential immediate and potential non-immediate analysis periods. For each treatment arm, the number and percentage of patients who experienced a TEAE of hypersensitivity or IRR will be reported.

The following summary tables may be provided about hypersensitivity/IRRS:

- treatment-emergent serious hypersensitivity, anaphylactic and IRRs
- potential immediate hypersensitivity, anaphylactic and IRRs by maximum severity
- potential non-immediate hypersensitivity, anaphylactic and IRRs by maximum severity
- symptoms for potential immediate hypersensitivity, anaphylactic and IRRs
- symptoms for potential non-immediate hypersensitivity, anaphylactic and IRRs.

4.6.8. Safety MRIs

Treatment-emergent white matter disease and other abnormality findings will be summarized as incidence in safety analysis set.

To evaluate white matter changes over time, a shift table from baseline to selected visits via treatment arm will be created from the following categories:

- 0 = No lesions
- 1 = Focal lesions
- 2 = Beginning confluence of lesions

• 3 = Diffuse involvement of entire region

4.7. Interim Analysis

An external Data Monitoring Committee (DMC) is authorized to evaluate results from unblinded interim analyses for the assessment of safety and futility and to recommend any modifications to the study (including stopping the study). Operational details and the decision rules will be provided in the DMC charter.

The DMC will have the responsibility to review accumulating unblinded study data and make recommendations to protect the safety of patients. The DMC will consist of a minimum of 3 members, including a physician with expertise in AD and a statistician. All members will be external to the Sponsor. The approved DMC charter enumerates the roles of the DMC members, the frequency with which it meets, and the structure of their meetings. Study sites will receive information about interim results ONLY if relevant for the safety of their patients.

For safety reviews, the DMC will receive data monitoring results that will include at least the following:

- Demographic characteristics of enrolled subjects
- Adherence to assigned treatment regimen
- Serious adverse events (SAEs)
- Non-serious adverse events
- Adverse events necessitating unblinding at the site or by the sponsor
- Vital signs data
- Central lab data
- Safety MRI data
 - Number of patients with significant treatment-emergent MRI findings, especially Amyloid Related Imaging Abnormalities (ARIA) events such as vasogenic edema or microhemorrhage
 - o Listing of all significant treatment-emergent MRI findings
 - o For patients with ARIA events, standard listings of medical history, concomitant medications, adverse events, baseline demographics
- C-SSRS data

At least 1 interim safety analysis may be conducted for the entire AACQ Study. Operational details and a quantitative framework to provide information for these decisions will be documented in interim analysis Statistical Analysis Plan.

5. Sample Size Determination

Approximately 800 participants will be randomly assigned to 1 of 4 treatment arms in a 1:1:1:1 ratio. It is hypothesized here that in each treatment arm, 10% of participants will not reach primary outcome lock. Below we showed that 720 participants who completed visit 12 can provide more than 80% power to demonstrate that there is over 80% probability that at least one of the alternative dosing regimens will reduce relative risk of ARIA-E by at least 20% compared to the standard dosing regimen.

The Bayesian power calculation was performed through simulations in both data generation and model fitting steps. In the data simulation stage, 1000 ARIA-E data sets were generated for every treatment arm. It was assumed that ARIA-E rate by Week 24 in the standard dosing regimen was 18.5% based on observations from AACI Addendum 9 data. In each alternative dosing regimen, ARIA-E rate was set to be equal to 11.1%, which translates to 40% relative risk reduction in ARIA-E compared to standard dosing regimen.

In the model fitting stage, a normal prior, N(0,4) was assigned to individual slope parameter of Arm 2, 3, and 4, respectively in the Bayesian logistic regression model. The intercept parameter was given a normal mixture prior, $0.5 \times N(-1.48, 4) + 0.5 \times N(-1.48, 30.19)$. The component prior mean (-1.48) in the mixture prior is equal to the natural log odds ratio of ARIA-E rate at 18.5% observed from historical study. For any simulated ARIA-E data with a complete sample size of 720, posterior samplers of RD_{21} , RD_{31} , and RD_{41} were simulated from 3 Markov chains with each chain composed of 10000 iterations after 10000 burn-ins. Among 1000 datasets generated, 927 satisfied at least one of the following probability statements:

```
Pr(RD_{21} \ge 0.2 \mid \text{simulated 24-week ARIA-E data}) > 0.8;

Pr(RD_{31} \ge 0.2 \mid \text{simulated 24-week ARIA-E data}) > 0.8;

Pr(RD_{41} \ge 0.2 \mid \text{simulated 24-week ARIA-E data}) > 0.8.
```

Hence, the reported power was 92.7% based on simulations.

In the null scenario where all the dosing regimens have the same true ARIA-E rate of 18.5% by Week 24, the false positive rate was controlled at 5% one-sided, or equivalently 10% two-sided.

The power and false-positive rate of the study were determined by simulations using R 4.1.2. Particularly, posterior samplers were generated through rjags package in R.

6. Supporting Documentation

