4.3.2. Main analytical approach

The number of ARIA-E events and the percentage of participants by treatment arm with any occurrence of ARIA-E events will be tabulated. The percentage of any occurrence of ARIA-E events is equivalent to ARIA-E incidence proportion. The primary analysis will use a Bayesian logistic regression model to estimate relative risk reduction in ARIA-E between alternative donanemab dosing regimen and standard donanemab dosing regimen given ARIA-E data up to Week 24.

The logistic regression model will include categorical effects of treatment arm, APOE e4 genotype, baseline presence of microhemorrhage, baseline presence of superficial siderosis, and baseline amyloid level. Treatment arm is a multinomial variable with 4 levels. APOE e4 genotype status has 3 levels: heterozygous carrier, homozygous carrier, and non-carrier. As participants with ≤4 microhemorrhages at baseline are eligible to enroll into this study, the model needs to adjust for baseline presence of microhemorrhage which is a binary predictor. The proposed model will also assess the impact of baseline presence of superficial siderosis because the study allows enrollment of eligible subjects with 1 area of cortical superficial siderosis. Baseline amyloid values are divided into terciles.

An integral part of Bayesian analysis is the formulation of prior distributions for regression coefficients. A diffuse prior will be assigned to all slope parameters to reflect the impact of the alternative dose regime and the effect of baseline covariates solely based on the data collected from the study. For the intercept parameter, a mixture prior will be using information on ARIA-E rates of the standard donanemab dosing regimen by 24 weeks from AACI – Addendum 9 study. The mixture prior will have a diffuse and an informative component. However, the informative component will have much less variability than the diffuse component. Both prior means are equal to log odds of the ARIA-E incidence in AACI-Addendum 9 study at Week 24. One normal prior has much less variability compared to another normal prior that is relatively flat. 50% weight will be assigned to each component of the mixture a priori.

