Through an iterative MCMC (Markov chain Monte Carlo) sampling method, a posterior distribution of ARIA-E incidence in Arm 1 (p_1) , Arm 2 (p_2) , Arm 3 (p_2) , or Arm 4 (p_4) at Week 24 will be simulated knowing the likelihood function of the logistic regression and prior density of individual regression coefficient. Afterwards, a posterior distribution of relative risk reduction in ARIA-E such as RD_{21} , RD_{31} , or RD_{41} as defined in Section 2 will be generated as well.

Posterior summary statistics, like posterior mean, posterior median, 2-sided equal-tailed 95% of posterior interval of RD_{21} , RD_{31} , or RD_{41} may be reported. The posterior probability of RD_{21} , RD_{31} , or RD_{41} being no smaller than 20% will be presented as well. The Bayesian logistic regression model can be implemented via both MCMC procedure in SAS and rjags package in R.

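### SAP Section 5 does not define the second argument of its priors, and under the reading that reproduces the 92.7% power the false-positive rate is about 6.1%, not 5%

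*SAP*

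**What the plan says.** The numeric priors appear only in SAP Section 5 (Sample Size Determination). There, "a normal prior, N(0,4) was assigned to individual slope parameter of Arm 2, 3, and 4", and "The intercept parameter was given a normal mixture prior", printed as 0.5 N(-1.48, 4) + 0.5 N(-1.48, 30.19). The second argument is not defined.

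SAP 4.3.2 describes the same priors in words. "A diffuse prior will be assigned to all slope parameters". The intercept mixture has an informative and a diffuse part, and "the informative component will have much less variability than the diffuse component". On software: "The Bayesian logistic regression model can be implemented via both MCMC procedure in SAS and rjags package in R".

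Section 5 claims that "720 participants who completed visit 12 can provide more than 80% power". It counts 927 successes in 1,000 simulated trials and concludes: "Hence, the reported power was 92.7% based on simulations". For the null with all arms at 18.5%, it says only that "the false positive rate was controlled at 5% one-sided, or equivalently 10% two-sided". It gives no simulated null count and no number of null replicates.

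Protocol 9.5 defines the false-positive rate as the chance that the critical success factor is met under the null. Protocol 9.1 says that factor is met when at least one alternative regimen passes, so the 5% is an any-arm rate. SAP 2.1 applies no multiplicity adjustment.

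**The concern.** Protocol 9.3.2 leaves the prior details to the SAP, and SAP 4.3.2 gives no numbers. A programmer would therefore take them from Section 5. In rjags the second argument of a normal is a precision; in SAS it can be coded as a variance. Copying the printed numbers could thus give two different primary analyses, and neither would match the description in 4.3.2.

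The second issue is the error rate. The 5% is the only error-rate claim for a success rule that gives three regimens a chance to pass without adjustment. If the prior that yields the stated power does not also yield 5%, the plan reports a more favourable operating characteristic than its rule has.

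**Working it through.** **Inputs.** From SAP Section 5: 180 analysed per arm (720 in total, after 10% loss from 800); 18.5% in the standard arm; 11.1% in each alternative arm for power; 18.5% in all arms for the null; the printed priors. From SAP Section 2 and Section 5: an arm succeeds if Pr(RD ≥ 0.2 | data) > 0.8, and the trial succeeds if any of the three arms does.

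**Step 1: what each convention implies.** The log odds of 18.5% are ln(0.185/0.815) = -1.48, which matches the prior mean. One patient at that rate carries information 0.185 × 0.815 = 0.1508 on the log-odds scale.

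- *All variance.* Slope SD is 2. Intercept SDs are √4 = 2 and √30.19 = 5.5. The tighter component has precision 1/4, worth 0.25/0.1508 = 1.7 patients, so neither component is informative.
- *All precision.* Slope SD is 1/√4 = 0.5. The assumed effect on the log-odds scale is ln(0.111/0.889) - ln(0.185/0.815) = -2.08 + 1.48 = -0.60. A prior SD smaller than the effect being sought is not diffuse.
- *4 as variance, 30.19 as precision.* Slope SD is 2. Intercept SDs are 2 and 1/√30.19 = 0.182. The second is worth 30.19/0.1508 = 200 patients. This fits every statement in 4.3.2.

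**Step 2: operating characteristics.** The model is the treatment-only logistic model of Section 5: logit(p1) = a, logit(pj) = a + bj, RDj1 = 1 - pj/p1. For each simulated trial the posterior was integrated numerically on a grid, without MCMC, using 60,000 to 400,000 trials per cell. Results at 180 per arm:

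| Reading of the second argument | Power | Any-arm false-positive rate |
|---|---|---|
| Slopes and first component variance, 30.19 precision | 92.7% | 6.1% |
| Slopes variance, both intercept components precision | 91.8% | 6.5% |
| Slopes SD 4, both intercept components precision | 92.8% | 6.8% |
| Slopes and first component SD 4, 30.19 precision | 94.3% | 6.2% |
| All variance | 84.6% | 8.5% |
| All SD | 85.3% | 8.8% |
| All precision | 73.7% | 2.3% |
| Slopes precision; intercept 4 variance, 30.19 precision | 76.4% | 2.2% |
| Slopes precision, intercept variance | 59.8% | 2.8% |

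Separate reruns of the main readings agreed within about 0.4 points. The first row used 400,000 trials, so the SE of its false-positive rate is √(0.061 × 0.939/400,000) = 0.04 points.

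The first row reproduces the SAP's 92.7%. Every reading within 2 points of that power gives a false-positive rate of 6.1% to 6.8%. Every reading at or below 5% has power under 80%, against the stated more than 80%. Under the first reading the per-arm rate is 2.2%. At 200 per arm it gives 94.1% power and an any-arm rate of 5.4%.

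**Step 3: could the 5% be simulation noise?** The null replicate count is not given. If it was 1,000 (assumption), the SE at 6.1% is √(0.061 × 0.939/1,000) = 0.76 points. A true 6.1% would then give 54 or fewer successes, and so print as 5% or less, about 20% of the time. With 10,000 replicates the SE is 0.24 points and that chance is about 0.5%.

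**Context.** The SAP claims control only at 18.5%. With common true rates of 14%, 16%, 21% and 25%, the first reading gives any-arm rates of 21.6%, 13.3%, 3.0% and 2.4%. With the flat intercept component alone (no borrowing), they are 11.5%, 9.8%, 6.8% and 4.9%. These do not contradict the SAP.

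**The case against.** The strongest reply is that 6.1% depends on an inferred prior. No document says that 4 is a variance and 30.19 a precision within one formula, and the sponsor's code is not available. The power match does not single out that reading: 927 of 1,000 has an SE of √(0.927 × 0.073/1,000) = 0.8 points, so several readings fit. This stands as a limit on the exact value. It does not rescue the 5%, because the other fitting readings give higher rates.

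The excess is about 1 point and may be noise or a carry-over. The SAP version history says power was recalculated for 10% discontinuation and does not mention the false-positive rate. Protocol 9.5 states the same 5% for 800 participants. At 200 per arm the rate is about 5.4%, which a 1,000-replicate run would print as 5% or less about 56% of the time. This is plausible, and it would mean the sentence is out of date at 720.

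Reading the 5% per arm does not help, because Protocol 9.5 ties it to the any-arm success factor.

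All-variance does make one intercept component less variable than the other (4 against 30.19) and leaves the slopes diffuse. It fails on having an informative component and on the power.

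The simulation omits APOE genotype, microhemorrhage, siderosis and amyloid terciles, all of which are in the primary model. So neither 5% nor 6.1% is the error rate of the full planned analysis. That stands, and it applies equally to the SAP's own figure.

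Finally, SAP 4.3.3 plans a neutral-prior sensitivity analysis, and Protocol 9.3.2 plans one without historical data. These help to interpret the result but do not define the primary prior.

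**Conclusion.** Wrong as written, on two counts. First, the printed priors cannot be run unambiguously, and neither uniform convention yields the analysis described in SAP 4.3.2. This rests on the text alone. Second, the stated 5% is not reproduced at 180 per arm. Under the reading that fits 4.3.2 and gives the stated power, the any-arm rate is about 6.1%, an excess of about 1 point. That value assumes the inferred mixed reading, a treatment-only model and a common true rate of 18.5%. Simulation noise or a carry-over from 200 per arm could explain the printed figure. The 92.7% power is not shown to be wrong.

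**What to change.** In SAP 4.3.2 and Section 5, state every prior as a mean and an SD. If the reading above is the intended one, that means slopes with mean 0 and SD 2, and an intercept prior of 0.5 N(mean -1.48, SD 0.182) + 0.5 N(mean -1.48, SD 2). If another was used, state that one.

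Rerun the null scenario at 180 per arm with at least 10,000 replicates. Replace the 5% statement with the simulated any-arm rate (about 6% if the reading is confirmed) and its replicate count, and say that the simulation model has no baseline covariates. Optionally, report the rate for common true rates on both sides of 18.5%, with and without borrowing.

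Leave the 0.80 threshold, the sample size and the design as they are. The cost is a few lines of SAP text, one simulation rerun, and a stated error rate about 1 point less favourable.
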